The smallest effect size that our proposed CRT design could detect with a specified statistical significance ($\alpha < 0.05$, two tailed) and statistical power ($1 - \beta = 80\%$ or higher) is known as the Minimum Detectable Effect Size (MDES) and can be calculated using Equation 1 adapted from Spybrook et al (2016). We estimated the MDES for our design using this equation and checked this using the PowerUp! software (Dong et al., 2015).

Equation 1:

$$MDES_{2LCRT} \sim M_{J-m-2} \sqrt{\frac{1}{P(1-P)}} \sqrt{\frac{ICC(1 - R_{Fam}^2)}{J} + \frac{(1 - ICC)(1 - R_{CYP}^2)}{nJ}}$$

For a CRT design, the MDES is influenced by:

- n = number of children per family (estimated as **2**); J = number of families (see below)
- P = proportion of families allocated to intervention group (**=0.50**)

- m = number of (level 2) covariates used (which will include: group membership, family-level pre-test and all variables used for minimisation, ~ 11 variables)
- M_{J-m-2} is the group effect multiplier value of the t-distribution for a 2-tailed test with $\alpha=0.05$ & $\beta=0.80$
- ICC is the family level ICC (proportion of variance of the outcome at level 2) ~ this is unknown but estimated at between 0.01 and 0.15 (to be updated with empirical estimates from internal pilot)
- R_{CYP}^2 = proportion of within-family child level variance that is reduced by covariate(s) - pupil level explanatory power and R_{Fam}^2 = proportion of between-family variance that is reduced by covariate(s) - family level explanatory power. These are also unknown and will be updated with empirical estimates from the internal pilot. For these a priori MDES estimates, we have assumed that $R_{CYP}^2 = R_{Fam}^2$ and allowed the values to vary between 0.25 and 0.49 (based on an assumed pre-post test correlation of between 0.50 and 0.70).

The number of families (J) has been allowed to vary between 200 and 350. This is the ITT sample of families without taking account of possible attrition (see below).

Table 3 shows a range of MDES estimates across 20 cells. MDES estimates of 0.22 SDs or lower are highlighted because, informed by meta-analyses of child outcomes for family therapy (van der Pol et al. (2017), parent mindfulness interventions (Burgdorf et al., 2019), and co-parenting interventions (Eira Nunes et al., 2020), we expect MBT-PP to produce a small effect on child outcomes.

Table 3. MDES estimates for a 2-level Clustered RCT with randomisation at the family level.

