We recommend a total sample size (pilot + efficacy) of 350 families to best ensure that the CRT design achieves an MDES of 0.22 SDs. In the event of zero attrition, a sample of 350 families (700 CYP) has MDES estimates between 0.15 and 0.20 SDs (depending on ICC and covariate explanatory power). With the assumption of 10% attrition, the randomised ITT sample of 350 would lead to a final sample of 315 families (630 CYP). Indicative MDES estimates for a sample of 315 families are between 0.16 and 0.21 SDs. Even in the event of attrition being 20%, the final sample (of 280 families, 560 CYP) results in indicative MDES estimates between 0.17 and 0.22 SDs. These indicative MDES estimates include an assumption that attrition will be random; which is why they are labelled as ‘indicative’. A missing data analysis will be undertaken to examine this assumption and, if appropriate, multiple imputation will be used to estimate missing values (within follow-on sensitivity analyses).

To combine the pilot and efficacy stage samples, the intervention needs to be as consistent as possible in both stages – although effect sizes for the two separate pilot and efficacy stages

will be reported alongside the combined effect size. Consistency in effect sizes along with the underlying Theory of Change would result in robust findings for the combined sample.

In addition to providing data to improve statistical sensitivity for the efficacy trial, the internal pilot would also be able to provide empirical estimates for both ICC and covariate explanatory power. This would allow the power analyses to be updated with empirical estimates (e.g., in the Statistical Analysis Plan).

In the pilot phase of the project we expect to reach and randomise 140 families (280 CYP). In the efficacy phase of the project, we expect to reach and randomise 210 families (420 CYP), making a total of 700 CYP over the entire recruitment phase (pilot + efficacy combined).

Table 4 has been completed assuming a total (pilot+efficacy) sample of 350 families (700 CYP). Please see above for details behind making this assumption. The estimations for pre-test/post-test correlations (family and CYP levels) and the ICC value (just family) cover a range of values. Data from the internal pilot will be used to update these with empirical estimates.

Table 4. Sample size calculations

		PARAMETER
Minimum Detectable Effect Size (MDES)		0.15 – 0.20, depending on ICC and covariate explanatory power

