- b) The acceptability of the referral pathways and consent and randomisation procedures to participants (indicated by drop out rates at these points)
- c) Whether there are any signs of problematic attrition (e.g. that might indicate that the research processes or interventions are not acceptable to participants)

- d) How the estimates used for the sample size calculation should be adjusted in light of data.

These aims inform the progression criteria (Appendix A), which utilise a red/amber/green classification system, whereby amber or red indicate that mitigations are required prior to progression.

Additional aims for the pilot study are:

- e) To pilot the data collection methods (including examining completion time and parent views on completing measures)
- f) To pilot data linking processes
- g) To seek early evidence supporting the Theory of Change
- h) To explore the relationship between parents' SDQ reports

Outcome measures

Certain features of the trial design mean that there is not a wide range of measures to choose from for many of our constructs. These include the age range of CYP targeted; 8-14 years is a wide age range and spans multiple developmental stages. Another feature that makes measure options limited is the fact that families may be intact or separated. Measures of IPC are typically intended for only one of these groups and are not appropriate for both. Finally, some of our constructs are only recently identified in the literature, or simply have not received a similar level of research attention as others, which means that only one measure exists (to the very best of our knowledge). Despite these challenges, we have selected a set of measures that are appropriate for the target population and have good psychometric properties.

All measures will be completed at baseline, post-intervention, and 3 month follow up.

Primary outcome

- a) The Strengths and Difficulties Questionnaire (SDQ; Goodman, 1997)

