^a First two months of referrals not included while referrers learn pathway. Project then delayed by set up difficulties, leading to a 4 month extension, hence percentage of eligible referrals to be counted from month 9-16.

Evaluation Measurement

Area	Question	Assessment method	Progression criteria	Red Amber Green
7. Overall recruitment to evaluation.	Have enough families been recruited? Is the project on track to meet the recruitment needed for the efficacy study?	Comparison of actual vs. required recruitment.	i) In months 3-12, 140 families are expected to have been recruited and randomised.	≥75% of target (105 families)
				74-50% of target (70-104 families)
				<50% of target (<69 families)
			ii) % of recruited families where both parents are participating	≥80% of recruited families (112 families)
				55-79% of recruited families (77-111 families)
				<55% of recruited families (<77 families)
8. Attrition from MBT-PP.	Have enough families that started MBT-PP completed the treatment protocol?	Therapist report of whether families were discharged before completing the treatment protocol i.e., before reaching the 'ending and signposting phase' of treatment.	% families who attended session 1 who were discharged before completing treatment protocol	<30% of families who attended session 1
				30-50%
				≥50%
9. Attrition from the evaluation.	Have enough parents and CYP completed the post-treatment outcome measures?	Comparison of actual vs. expected attrition from the evaluation (completing post-treatment outcome measures).	i) Attrition of Parent 1 (provider of primary outcome measure) across study arms.	≤10% of those recruited and randomised
				11-30%
				>30%
	Does attrition differ systematically between study arms?		ii) Percentage of Parent 1s who were lost from evaluation who were in MBT-PP condition (aiming for approx. half).	45-55%
				35-44% or 56-65%
				<35% or >65%

			iii) Attrition of Parent 2s (who completed baseline measures) across study arms.	
≤10% of those recruited and randomised
 
11-30%
 
>30%

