			iv) Percentage of Parent 2s who were lost from evaluation who were in MBT-PP condition (aiming for approx. half).	
45-55%
 
35-44% or 56-65%
 
<35% or >65%

			v) Attrition of CYP (who completed baseline measures) across study arms.	
≤10%
 
11-30%
 
>30%

			vi) Percentage of CYP who were lost from evaluation who were in MBT-PP condition (aiming for approx. half).	
45-55%
 
35-44% or 56-65%
 
<35% or >65%

Measurement and findings

Area	Question	Assessment method	Progression criteria	Red Amber Green
10. Acceptability/		Calculate proportions of participants allocated to each condition.	% participants allocated to MBT-PP	
45-55%
 
35-44% or 56-65%

feasibility of randomisation.	Did randomisation work? Were there any problems?	Reflections on randomisation process from SHU, TR and LAs.	Degree of problems reported with randomisation process.	<35% or >65%
				No problems.
				Minor problems, refinements to processes needed.
				Significant problems, major changes to processes needed.
11. Data quality.	Is the baseline and post-treatment primary outcome measure data of high quality?	Calculate amount of missing data within SDQ responses that have been collected	% missing data within the 25 SDQ items completed by parents at baseline and post-treatment	≤10%
				10-30%
				>30%
12. Effective use of core measures.	Is there an effective mechanism in place to collect the outcome measures?	Report mechanisms for collecting outcome measures.	Mechanisms in place to collect outcome measures from parents and CYP.	A Gateway Lead is in post in each LA to liaise with evaluator for the completion of baseline, post-treatment and follow-up outcome measures.

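### Progression criteria 9 ii, iv and vi judge differential attrition by the share of losses in the MBT-PP arm, which is mostly noise at the expected numbers and does not measure the gap between arms

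*Protocol*

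**What the plan says.** Appendix A, criterion 9, asks "Does attrition differ systematically between study arms". Three sub-criteria address that question:

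- 9 ii: "Percentage of Parent 1s who were lost from evaluation who were in MBT-PP condition (aiming for approx. half")
- 9 iv: "Percentage of Parent 2s who were lost from evaluation who were in MBT-PP condition (aiming for approx. half")
- 9 vi: "Percentage of CYP who were lost from evaluation who were in MBT-PP condition (aiming for approx. half")

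All three use the same bands: green 45-55%, amber 35-44% or 56-65%, red below 35% or above 65%. Overall attrition is rated separately and pooled across arms in 9 i, iii and v. For Parent 1 the green limit in 9 i is "≤10% of those recruited and randomised".

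Appendix A gives no attrition rate by arm, no difference, no interval, no minimum number of losses and no error rate for the bands. The colours have consequences: under Internal Pilot Study the protocol says that "amber or red indicate that mitigations are required prior to progression". The history entry for version 3.1 names assessment of systematic differences between arms as one purpose of the rewording.

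**The concern.** The measure looks only at those who were lost and ignores how many were randomised or retained in each arm. Two problems follow.

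First, at low attrition the denominator is a handful of people. A 45-55% band then contains one possible count or none, so two arms with identical attrition will usually be flagged.

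Second, a share of losses is a relative measure. The same share corresponds to a small gap in percentage points when attrition is low and a large one when it is high. It also moves with the allocation ratio.

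At stake is a formal progression rating that triggers mitigation, and what the pilot and final reports then say about attrition bias.

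**Working it through.** **Inputs from the documents.** Pilot size: "In the pilot phase of the project we expect to reach and randomise 140 families (280 CYP"). Allocation: "P = proportion of families allocated to intervention group (=0.50"), so about 70 families per arm. Planned attrition is 10% (Protocol, Assumptions), which is also the green limit in 9 i. The SAP's sample size section uses 90 families at pilot. Criterion 7 ii sets its green limit at 112 two-parent families.

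**Plan's own figures.** 350 × 0.90 = 315 families and 0.75 × 140 = 105 families, both as stated. The plan gives no figure for how the 9 ii, iv and vi bands perform, so there is none to reproduce.

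**Losses expected at 10%.** Parent 1: 0.10 × 140 = 14. With 90 families: 9. Parent 2: 0.10 × 112 ≈ 11. Children: 0.10 × 280 = 28.

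**No true difference, given the number of losses.** With 1:1 allocation, the losses in MBT-PP out of L are approximately Binomial(L, 0.5). Percentages are rounded to whole numbers to fit the printed bands.

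- L = 14: only 7:7 is green, C(14,7)/2^14 = 3432/16384 = 21%. Amber is 5, 6, 8 or 9: 10010/16384 = 61%. Red is the remaining 2942/16384 = 18%.
- L = 9: the nearest splits are 4/9 = 44.4% and 5/9 = 55.6%, neither green. Amber 252/512 = 49%, red 260/512 = 51%.
- L = 11: green 45%, amber 32%, red 23%.
- L = 28: green 43%, amber 48%, red 9%. This treats children as independent; losses clustered in families make 9 vi noisier.

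**No true difference, number of losses left random.** Two independent binomials, 70 per arm, exact. Rates other than 10% are assumptions.

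| True attrition, both arms | Green | Amber | Red |
|---|---|---|---|
| 5% | 18% | 34% | 47% |
| 10% | 31% | 45% | 24% |
| 20% | 47% | 46% | 7% |
| 30% | 60% | 38% | 2% |

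The rating of equal attrition improves as retention worsens.

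**What a given share means.** Let a be overall attrition and s the MBT-PP share of losses. With 1:1 allocation the arm rates are 2as and 2a(1 − s), so the gap is 2a(2s − 1). For s = 0.65:

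- a = 0.10 gives 13% v 7%, a gap of 6 points;
- a = 0.30 gives 39% v 21%, a gap of 18 points.

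Both get the same colour. With unequal allocation the share is also displaced: a 60:40 split, amber under criterion 10, gives an expected share of 60% with equal attrition.

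**A real 10-point gap, 70 per arm.** The documents give no rates by arm, so these are assumptions.

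| MBT-PP v TAU | Expected share | Green | Amber | Red |
|---|---|---|---|---|
| 15% v 5% | 75% | 4% | 15% | 81% |
| 20% v 10% | 67% | 11% | 35% | 55% |
| 30% v 20% | 60% | 24% | 52% | 24% |
| 35% v 25% | 58% | 31% | 56% | 14% |
| 40% v 30% | 57% | 37% | 56% | 7% |

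For a constant gap, sensitivity falls as overall attrition rises.

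**Precision of the direct comparison.** The 95% half-width is 1.96 × √(2p(1 − p)/70): ±9.9 points at p = 10%, ±13.3 at 20%, ±15.2 at 30%.

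**The case against.** A reader might go further and infer that the criterion often lets a real difference through. At the planned attrition the documents do not support that. Amber as well as red calls for mitigation, so only green is a miss, and a 10-point gap is green 4% of the time at 15% v 5% and 11% at 20% v 10%. Misses become common only when overall attrition is around 30%, three times the plan, and there 9 i would already be amber or red.

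A reader might also call the rating meaningless. It is not: with 1:1 allocation the share tracks the ratio of the two attrition rates, and 15% v 5% is red 81% of the time. It is a noisy screen on a relative scale.

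Nor does the final analysis inherit the problem. Nothing in the SAP uses criterion 9. The SAP repeats the baseline comparison by arm on complete cases, describes missingness across the variables in the main model, fits a drop-out model and, if that model finds predictors, imputes. The protocol's risk register promises a CONSORT diagram for attrition. Amber and red lead to mitigation, not stopping, and these are three items in a list of twelve areas.

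Two further objections stand in part. Percentage-point bands are not plainly better. With 5 and 10 points as cut-offs and 70 per arm, equal attrition of 10% is green 68% of the time instead of 31%. But 15% v 5% is green 16% instead of 4%, and equal attrition of 30% is red 17% instead of 2%. On timing, the protocol places the progression decision in late June 2024 and SAP version 1.1 is dated January 2025, so on that timetable the practical effect is mainly on reporting.

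What these objections leave untouched is the behaviour at the expected numbers with no difference between arms.

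**Conclusion.** The concern holds as a fault of scale and noise. At 10% attrition, arms that do not differ fail to reach green 79% of the time given 14 losses, or 69% with the number of losses left random (70 per arm), and are red 18% and 24% of the time respectively. With 9 losses green is impossible. The share cannot be read as a gap without the overall attrition and the allocation ratio, so it is a poor answer to the question criterion 9 asks.

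The false-alarm figures at 14 and 9 losses rest on the protocol's and SAP's own numbers, on rounding to whole percentages and on independent losses. The figures for real gaps rest on assumed rates by arm. The consequence is confined to the pilot rating, the mitigation it triggers and any attrition statement that relies on the colours. The primary effect estimate and its test are not affected.

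**What to change.** Base 9 ii, iv and vi on attrition in each arm and the difference (MBT-PP minus TAU) with a 95% CI. The denominator is those randomised for Parent 1, and those with baseline measures for Parent 2 and for children. The interval for children should allow for clustering in families. Do not rely on the share-of-losses colours in the pilot or final report; if they have already been reported, set the rates and difference beside them.

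If colour bands are kept, the evaluator should choose percentage-point limits and show their error rates at the expected sample size, both for no difference and for a gap judged important.

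The cost is the rewording of three criteria; the counts are already held. The downside is that the pilot remains imprecise: about ±10 points at 10% attrition with 70 per arm. Bands such as 5 and 10 points would reduce false alarms at low attrition but miss somewhat more real gaps there.

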STATISTICAL ANALYSIS PLAN

Evaluation of Tavistock Relationships MBT-PP to improve child outcomes by reducing inter-parental conflict: a pragmatic efficacy randomised controlled trial with internal pilot

Sheffield Hallam University

Principal investigator: [name]

Evaluation of Tavistock Relationships MBT-PP to improve child outcomes by reducing inter-parental conflict: a pragmatic efficacy cluster randomised controlled trial with internal pilot
Statistical analysis plan

Evaluating institution: Sheffield Hallam University

Principal investigator(s): [name]

Project title	Evaluation of Tavistock Relationships MBT-PP to improve child outcomes by reducing inter-parental conflict: a pragmatic efficacy cluster randomised controlled trial with internal pilot
Developer (Institution)	Tavistock Relationships
Evaluator (Institution)	Sheffield Hallam University
Principal investigator(s)	[name]
SAP author(s)	[name], [name], [name], [name]
Trial design	Two armed balanced 2 level clustered RCT with children clustered into (referred) families and randomisation at the family level.
Trial type	Efficacy with internal pilot
Evaluation setting	3 x local authorities (Bristol, Bournemouth, Christchurch & Poole (BCP) and Dorset). Intervention will be embedded into Early Help, creating a 'reducing parental conflict' referral pathway
Target group	Families with children/young people aged 7-14 experiencing inter-parental conflict
Number of participants	Protocol

Primary outcome and data source	Child externalising and internalising problems (as measured by the mothers reported SDQ 'total difficulties' scale)
Secondary outcome and data source	Inter-parental conflict (parent report and child report) Child psychological well-being (child report) Parenting style (parent report) Parent mentalising capacity (parent report) Parent anger expression (parent report) Parent emotional adaptation (parent report)

SAP version history

Version	Date	Changes made and reason for revision
1.1 [latest]	17/01/25	Responding to reviewer comments.
1.0 [original]		[leave blank for the original version]

Interparental conflict (IPC), regardless of whether parents are still together or separated/divorced, has long lasting negative impacts on children and young people (CYP), including contributing to emotional and behavioural problems (van Eldik et al., 2020). The intervention under evaluation in this efficacy trial is Mentalization Based Therapy for Parenting Under Pressure (MBT-PP), delivered by Tavistock Relationships. MBT-PP is a 10-session intervention delivered over 16 weeks, to parents experiencing high conflict, by a trained therapist. Sessions are delivered online and are, after individual assessment sessions, attended by both parents simultaneously if possible. There is no direct therapeutic work with CYP. MBT-PP is offered to parents experiencing high levels of intense and poorly resolved conflict. The goal of MBT-PP is to help parents to reduce their conflict, which is expected to lead to improved outcomes for CYP. The theory of change for MBT-PP is that by increasing parents' capacity to mentalise (think about the thoughts and feelings of the other person, in real time) about their co-parent's and their child(ren)'s experience, parents become more aware of the emotional impact of their conflict on their child(ren), and express less anger towards their co-parent (Hertzmann et al., 2016). They may also become more emotionally adapted to the reality of their situation (e.g., if newly separated). This should lead to a reduced level of conflict between parents (Millings et al., 2020), which means that CYP perceive less conflict between parents. CYP then have fewer experiences of blaming themselves for, or fearing becoming the target of the conflict, which in turn leads to CYP having fewer emotional and behavioural problems, and better overall psychological well-being.

Design overview

This pragmatic efficacy trial with internal pilot is a two-armed balanced 2 level clustered RCT, in which MBT-PP is compared against Treatment As Usual (TAU). TAU is support for interparental conflict based around the digital resources 'Getting It Right for Children' for separated parents, and 'Argue Better' for intact parents. Both resources are created by OnePlusOne and are designed to be used as guided self-help, in which clients work through the materials and also check in with a practitioner about their progress (Cavanagh & Millings, 2013). TAU is delivered by local authority staff.

This trial is running in 3 local authorities, Bristol, Dorset, and Bournemouth, Christchurch, and Poole (BCP). In each local authority, this evaluation funds a 'Gateway Lead' post. Postholders are staff with experience of working with CYP and families and have backgrounds in primary teaching and family support.

Gateway Leads have created referral pathways into the project and promoted awareness of the project in schools and other relevant local authority staff. When referred, families are screened for eligibility against exclusion and inclusion criteria and taken through the consent

process. Once consent is obtained, families complete baseline assessments, and are subsequently randomly allocated to receive either MBT-PP or TAU. Allocation is conducted by the evaluator according to a minimisation protocol to ensure a balanced sample. Families then undergo their allocated treatment. Once treatment has completed, families complete post-intervention assessments. Follow up assessments are completed 3 months later.

The primary outcome variable for this trial is the ‘Total Difficulties’ (TD) subscale of the Strengths and Difficulties Questionnaire (SDQ; Goodman, 1997) obtained from the mothers’ post-intervention assessment, reporting on the CYP. As such, analyses will focus on comparing mothers’ post-intervention TD scores between MBT-PP and TAU. Secondary outcome variables are fathers’ post-intervention TD score; and child psychological well-being (as measured by the Stirling Children’s Well-being Scale, Liddle & Carter, 2015).

The trial is also assessing proposed mechanisms of action, by assessing: parent report IPC (as measured by the O’Leary-Porter Scale, OPS, Porter & O’Leary, 1980, adapted as described in the protocol); child perception of IPC (as measured by the Perceptions of Interparental Conflict-Intensity/Frequency Scale, PIC-I/F, Kline, Wood & Moore, 2003); parent anger (as measured by the Dimensions of Anger Reactions-Revised, DAR-R, Nederlof et al., 2009); parent mentalising capacity (as measured by the Parental Reflective Function Questionnaire, PRFQ, Luyten et al., 2009); parenting style (as measured by the Parenting Scale Short Form, PS-8, Kliem et al., 2019); and, for separated parents only, parent emotional adaptation to separation (as measured by the Emotional Adaptation to Relationship Dissolution Assessment, EARDA, Millings et al., 2020).

Table 1. Trial design overview

Trial design, including number of arms		Two armed balanced 2 level clustered RCT with children clustered into (referred) families and randomisation at the family level.
Unit of randomisation		Family
Stratification variables (if applicable)		Age group (all CYP aged 8-11 / all CYP aged 12-14 / CYP aged 8-11 and 12-14), Minority ethnic group status of one or both parents (yes / no), relationship status (separated/intact)
Primary outcome	Variable	a) Child internalising and externalising behaviours
	Measure (instrument, source, scale)	a) Mother reported SDQ, total difficulties scale (Goodman, 1997). Scale 0 to 40.
Secondary outcome(s)	Variable(s)	b) Child psychological well-being c) Parent report IPC

		
d) Child perception of IPC
 
e) Parent anger
 
f) Parent mentalising capacity
 
g) Parenting style
 
h) Parent emotional adaptation to separation (separated parents only)

	
Measure(s) (instrument, source, scale)
	
b) Stirling Children’s Well-being Scale (SCWBS; Liddle & Carter, 2015). Scale 12 to 60.
 
c) O’Leary-Porter Scale (OPS; Porter & O’Leary, 1980). Scale 0 to 40.
 
d) Perceptions of Interparental Conflict-Intensity/Frequency Scale (PIC-I/F; Kline, Wood & Moore, 2003). Scale 13 to 78.
 
e) Dimensions of Anger Reactions- Revised (DAR-R; Nederlof, Hovens, Muris & Novaco, 2009). Scale 0 to 28.
 
f) Parental Reflective Function Questionnaire (PRFQ; Luyten et al., 2009). Scale 1 to 7.
 
g) Parenting Scale Short Form (PS-8; Kliem et al., 2019), a short form of the Parenting Scale (Arnold et al., 1993). Scale 1 to 7.
 
h) Emotional Adaptation to Relationship Dissolution Assessment (EARDA; Millings et al., 2020). Scale 0 to 5.

Baseline for primary outcome	Variable	Scores at baseline (pre-randomisation) on variable listed above
	Measure (instrument, source, scale)	As above
Baseline for secondary outcome	Variable(s)	Scores at baseline (pre-randomisation) on variables listed above
	Measure(s) (instrument, source, scale)	As above

Sample size calculations

Table 2. Sample size calculations overview

		Protocol	SAP (drawing on empirical estimates for explanatory power and ICC)
Minimum Detectable Effect Size (MDES)		0.15-0.20 sds	0.17 sds
Pre-test/ post-test correlations	Level 1 (participant)	0.50 to 0.70 (R^2 between 0.25 & 0.49)	0.87 ($R^2 = 0.75$)
	Level 2 (cluster)	0.50 to 0.70 (R^2 between 0.25 & 0.49)	0.78 ($R^2 = 0.61$)
Intracluster correlations (ICCs)	Level 1 (participant)	n/a	n/a
	Level 3 (cluster)	0.01 to 0.15	0.27
Alpha		0.05	0.05
Power		0.80	0.80
One-sided or two-sided?		Two	Two
Average cluster size		2 CYP per family	1.4 CYP per family
Number of clusters	Intervention	175	125
	Control	175	125
	Total	350	250
Number of participants (CYP)	Intervention	350	175
	Control	350	175
	Total	700	350

The power analyses published in the protocol included key parameters for which no empirical estimates could be obtained. Specifically, these were covariate explanatory power (from the baseline mothers SDQ measure) at CYP and family levels and the family level ICC for the mothers SDQ measure at outcome. The protocol used relatively wide ranges of values for CYP and family level explanatory power (between 0.25 and 0.49) and ICC (0.01 to 0.15).

As specified in the protocol, analyses of data from the internal pilot provides empirical point estimates for these parameters for use in the updated power analyses presented here. At the time of writing (August 2024), a total of 43 families (21 allocated to MBT and 22 to TAU) with 61 CYP (30 MBT, 31 TAU) had complete baseline/T1 and outcome (T2, post intervention) mothers SDQ. Analyses of these 61 CYP in 43 families has been used to provide empirical estimates for ICC and explanatory power at the family and CYP levels.

The power analyses were undertaken using equation 1.0 below and checked using the PowerUp! software (Dong & Maynard, 2013, sheet CRA2_2r).

$$[1.0] \quad MDES_{2LCRT} \sim M_{J-m-2} \sqrt{\frac{1}{P(1-P)}} \sqrt{\frac{ICC(1-R_{Fam}^2)}{J} + \frac{(1-ICC)(1-R_{CYP}^2)}{nJ}}$$

For a 2-level CRT design, the MDES is influenced by (estimates updated from analyses of pilot data):

- n=number of CYP per family = **1.4** (updated from 2.0 in protocol).
- J = number of families (**90** at pilot, allowed to vary up to **400** see below).
- P = proportion of families allocated to intervention group (= **0.50**).
- m= number of (level 2) covariates used (which will include: group membership, family-level pre-test, 4 (dummy) variables used for minimisation ~ **6** variables).
- M_{J-m-2} is the group effect multiplier value of the t-distribution for a 2-tailed test with alpha=0.05 & beta=0.80.
- ICC is the family level ICC = **0.27** (updated from 0.01 to 0.15 in protocol). This is the proportion of variance of the outcome at level 2 (between-family variance).
- $R_{CYP}^2 = 0.75$ (updated from 0.25 to 0.49 in protocol). The proportion of within-family child level variance that is reduced by covariate(s). This is the within-family, between-CYP explanatory power.
- $R_{Fam}^2 = 0.61$ (updated from 0.25 to 0.49 in protocol). The proportion of between-family variance that is reduced by covariate(s) – between-family explanatory power.

Four changes between the protocol and SAP have been made. As shown in equation 1, two of these (reduced CYP per family and increased ICC) will result in reducing the statistical sensitivity of the clustered RCT design. At the same time, two changes (increased explanatory power at CYP and family levels) will result in increasing the statistical sensitivity. To illustrate

the differences, Table 3 shows MDES estimates for a range of sample sizes from power analyses presented in the protocol and updated in this SAP.

Table 3. Sample sizes and MDES estimates for the protocol and SAP stages of the Tavistock MBT-PP impact evaluation

MDES estimates	Protocol	SAP
	
 • 2.0 CYP per family • ICC ~ 0.01-0.15 • CYP explanatory power ~ 0.25-0.49 • Fam explanatory power ~ 0.25-0.49 	
 • 1.4 CYP per family • ICC = 0.27 • CYP explanatory power = 0.75 • Fam explanatory power = 0.61
90 Families	0.30-0.40	0.29
150 Families	0.23-0.31	0.22
200 Families	0.20-0.27	0.19
250 Families	0.18-0.24	0.17
300 Families	0.16-0.22	0.16
350 Families	0.15-0.20	0.15
400 Families	0.14-0.19	0.14

The SAP power analyses resulted in MDES estimates closer to the lower range estimates presented in the protocol. At protocol stage, it was decided that 350 families (with 700 CYP) would be required for the clustered RCT design to be able to detect an effect size of 0.20 or higher as statistically significant ($p < 0.05$, two-tailed) with a statistical power of 0.80 or higher. With 350 families, the MDES estimates ranged between 0.15 and 0.20 sds (depending in the ICC and explanatory power). With an attrition rate of 10%, assuming attrition was random, the indicative MDES estimates ranged between 0.16 and 0.21 sds. With an attrition rate of 20%, assuming attrition was random, the indicative MDES estimates ranged between 0.17 and 0.23 sds.

The updated power analyses presented here illustrate that, even with fewer CYP per family than initially estimated, a smaller sample of families is likely to be sufficient sensitivity to detect an MDES of 0.20 sds or higher than was estimated at protocol. With 250 families (and 350 CYP), the MDES estimate is 0.17 sds. With an attrition rate of 10%, assuming attrition was random, the indicative MDES estimate is 0.18 sds. With an attrition rate of 20%, assuming attrition was random, the indicative MDES estimate is 0.19 sds.

Therefore, following the updated power analysis, the recommended sample size for the evaluation of the Tavistock MBT-PP programme is reduced from 350 families (700 CYP) to be 250 families (350 CYP).

Analysis

Research questions were operationalised as follows:

RQ1 Does MBT-PP (compared to TAU) delivered to parents experiencing IPC lead to lower externalising and internalising behaviours in children aged 8-14 (as measured by the SDQ total 'difficulties' scale)?

This splits into two separate RQs (SDQ total difficulties for mothers and for fathers).

RQ1a Does MBT-PP (compared to TAU) delivered to parents experiencing IPC lead to lower externalising and internalising behaviours in children aged 8-14 as measured by the mother's SDQ total 'difficulties' scale? – PRIMARY OUTCOME RQ1

RQ1b Does MBT-PP (compared to TAU) delivered to parents experiencing IPC lead to lower externalising and internalising behaviours in children aged 8-14 as measured by the father's SDQ total 'difficulties' scale? – SECONDARY OUTCOME RQ1

RQs 2-8 inclusive also all examine secondary outcomes, and, apart from those where the outcome variable comes from CYP rather than parents (RQ2 regarding child wellbeing and RQ4 regarding child perception of IPC), they split into a) maternal report and b) paternal report, as per RQ1.

RQ2 Does MBT-PP (compared to TAU) delivered to parents experiencing IPC lead to higher wellbeing in children aged 8-14 (as measured by the Stirling Children's Well-being Scale)?

RQ3 Does MBT-PP (compared to TAU) delivered to parents experiencing IPC lead to lower IPC reported by parents (as measured by the O-Leary-Porter Scale)?

RQ3a Does MBT-PP (compared to TAU) delivered to parents experiencing IPC lead to lower IPC reported by mothers (as measured by the O-Leary-Porter Scale)?

RQ3b Does MBT-PP (compared to TAU) delivered to parents experiencing IPC lead to lower IPC reported by fathers (as measured by the O-Leary-Porter Scale)?

RQ4 Does MBT-PP (compared to TAU) delivered to parents experiencing IPC lead to lower IPC reported by children (as measured by the Children's Perception of Interparental Conflict Scale)?

RQ5 Does MBT-PP (compared to TAU) delivered to parents experiencing IPC lead to lower parent anger expression (as reported by the Dimensions of Anger Reactions-Revised)?

RQ5a Does MBT-PP (compared to TAU) delivered to parents experiencing IPC lead to lower mother anger expression (as reported by the Dimensions of Anger Reactions-Revised)?

RQ5b Does MBT-PP (compared to TAU) delivered to parents experiencing IPC lead to lower father anger expression (as reported by the Dimensions of Anger Reactions-Revised)?

RQ6 Does MBT-PP (compared to TAU) delivered to parents experiencing IPC lead to higher mentalising ability in parents (as reported by the Parental Reflective Function Questionnaire)?

RQ6a Does MBT-PP (compared to TAU) delivered to parents experiencing IPC lead to higher mentalising ability in mothers (as reported by the Parental Reflective Function Questionnaire)?

RQ6b Does MBT-PP (compared to TAU) delivered to parents experiencing IPC lead to higher mentalising ability in fathers (as reported by the Parental Reflective Function Questionnaire)?

RQ7 Does MBT-PP (compared to TAU) delivered to parents experiencing IPC lead to more positive parenting (as measured by the Parenting Scale Short Form PS-8)?

RQ7a Does MBT-PP (compared to TAU) delivered to parents experiencing IPC lead to more positive parenting by mothers (as measured by the Parenting Scale Short Form PS-8)?

RQ7b Does MBT-PP (compared to TAU) delivered to parents experiencing IPC lead to more positive parenting by fathers (as measured by the Parenting Scale Short Form PS-8)?

RQ8 Does MBT-PP (compared to TAU) delivered to separated parents experiencing IPC lead to better parent emotional adaptation to relationship dissolution (as measured by the EARDA)?

RQ8a Does MBT-PP (compared to TAU) delivered to separated parents experiencing IPC lead to better mother emotional adaptation to relationship dissolution (as measured by the EARDA)?

RQ8b Does MBT-PP (compared to TAU) delivered to separated parents experiencing IPC lead to better father emotional adaptation to relationship dissolution (as measured by the EARDA)?

Error! Not a valid bookmark self-reference. presents the primary and secondary outcomes for the Tavistock MBT-PP impact evaluation.

